### Timeline in ED

ED LOS  
LOS after being roomed  
Time to discharge  
Time the resident physician spent in room  
Time to perform ultrasound  
Diagnosis of dislocation/initial evaluation  
Confirmation of reduction

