## II. STUDY OBJECTIVE(S); INCLUDING SPECIFIC AIMS AND/OR HYPOTHESES

The primary objective of this study is to determine if there is any difference in the length of stay between patients with shoulder dislocation who are treated with traditional x-ray imaging for diagnosis and reduction confirmation and those that are treated with POCUS for diagnosis and reduction confirmation.

*Hypothesis:* The use of POCUS for shoulder dislocation and reduction confirmation will reduce the length of stay for ED patients.

The secondary objectives of this study include evaluating patient satisfaction, providing a cost analysis, time to diagnosis, confirmation of reduction, and volume of x-ray reduction.

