### Procedural Overview/Design:

1. Assess patient for enrollment. Apply inclusion and exclusion criteria (below).
2. Discuss Informed consent with patient. If patient consents, proceed to step 3.
3. Randomize patient with premade numbered envelopes stating standard of care or ultrasound protocol (description below).

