#### B. Statistical Methodology

Descriptive statistics will be used to evaluate demographic variables. Categorical variables will be reported as n (%) and will be analyzed by chi-square or Fisher's exact test as appropriate. Normally distributed continuous variables will be reported as mean and standard deviation and will be analyzed by student's t-test. Non-normally distributed continuous variables will be reported as medians and interquartile range and analyzed using Mann-Whitney U test. The primary outcome of difference in average length of stay in the ED will be analyzed by paired students T-test. Secondary outcomes will be evaluated by paired student t-tests as well. Statistical analysis will be performed using SPSS® Software (version 24; 2016) and the level of significance set at p value less than 0.05.

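### The primary analysis of ED length of stay makes no adjustment for time that elapses before randomisation, which costs precision but does not cause bias

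*Combined protocol and SAP*

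**What the plan says.** The primary objective is to "determine if there is any difference in the length of stay between patients with shoulder dislocation", comparing x-ray with point-of-care ultrasound. Section V.B states: "The primary outcome of difference in average length of stay in the ED will be analyzed by paired students T-test". No covariate is named there for any outcome.

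The Timeline in ED list under Data Collection has three overall clocks: ED LOS, "LOS after being roomed" and "Time to discharge". None has a defined start or stop. The second and third appear in neither the statistical methods nor the secondary objectives, which are "evaluating patient satisfaction, providing a cost analysis, time to diagnosis, confirmation of reduction, and volume of x-ray reduction".

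The Procedural Overview gives the order of events. Step 1 is "Assess patient for enrollment. Apply inclusion and exclusion criteria (below"), step 2 is consent, and step 3 is "Randomize patient with premade numbered envelopes stating standard of care or ultrasound protocol". The documents do not say whether this happens before or after the patient is roomed.

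**The concern.** If ED length of stay runs from arrival, it is the sum of two parts: the time up to the opening of the envelope and the time after it. Only the second part can respond to the imaging strategy. The first part contributes patient-to-patient variation and no treatment signal, and an unadjusted comparison of totals carries that variation into the standard error.

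Precision matters here. Enrolment is bounded by calendar dates (August 1, 2020 to December 31, 2022), the plan calls the injury infrequent, and Section V.A gives no target sample size. Precision lost in the analysis cannot readily be regained by enrolling more patients. Most of what is needed to recover it is already being abstracted or is one timestamp away.

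**Working it through.** **No planned figure to reproduce.** The plan states no sample size, power, SD, allocation ratio or target effect. What follows is illustration.

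**Inputs**
- Effect: 30 minutes. This is the increase in length of stay that the Background attributes to diagnostic radiographs in one cited study. It is not a planned target.
- Alpha: 0.05 from Section V.B, taken as two-sided.
- Assumed, not in the documents: 80% power, 1:1 allocation, independent arms, total SD of 90 or 120 minutes, SD of the pre-randomisation wait of 30 or 60 minutes, and (at first) no correlation between the wait and later time.

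**Step 1: sample size.** With zero correlation, residual variance after adjustment = SD_total² − SD_wait². Sample size per arm = 2(1.96 + 0.8416)² × variance / 30² = 15.70 × variance / 900, rounded up. Power at 100 per arm (a round number for comparison only) uses the normal approximation: Φ(30 / √(2 × variance / 100) − 1.96).

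| Total SD | Wait SD | Variance | n per arm | Reduction | Power at 100 per arm |
|---|---|---|---|---|---|
| 90 | unadjusted | 8100 | 141.3 → 142 | – | 0.65 |
| 90 | 30 | 7200 | 125.6 → 126 | 900/8100 = 11% | 0.71 |
| 90 | 60 | 4500 | 78.5 → 79 | 3600/8100 = 44% | 0.89 |
| 120 | unadjusted | 14400 | 251.2 → 252 | – | 0.42 |
| 120 | 30 | 13500 | 235.5 → 236 | 900/14400 = 6% | 0.45 |
| 120 | 60 | 10800 | 188.4 → 189 | 3600/14400 = 25% | 0.53 |

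**Step 2: dependence on the correlation.** Let SD_post be the SD of the time after the wait and r its correlation with the wait.
- Unadjusted variance = SD_post² + SD_wait² + 2r × SD_post × SD_wait.
- Adjusted variance = SD_post²(1 − r²).
- Difference = (SD_wait + r × SD_post)², which is never negative.

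With SD_post 90 and SD_wait 60, the ratio of unadjusted to adjusted variance is:
- r = +0.3: 14940 / 7371 = 2.03
- r = 0: 11700 / 8100 = 1.44
- r = −0.3: 8460 / 7371 = 1.15
- r = −0.5: 6300 / 6075 = 1.04

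The gain reaches zero at r = −60/90 = −0.67. Apart from the one degree of freedom spent on the covariate, adjustment does not do worse than the unadjusted analysis.

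**Step 3: contrast with switching the endpoint.** Replacing ED length of stay by post-rooming time is a different choice, and it can lose precision. Treat the wait as arrival to rooming, with the same SDs and r = −0.5. Total length of stay then needs 110 per arm and post-rooming time needs 142 (110/142 = 0.77). This is a reason to adjust the total rather than replace it.

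**The case against.** The strongest reply is that nothing here threatens validity. If the wait precedes allocation, randomisation balances it in expectation and the unadjusted difference is unbiased. Total ED length of stay is also a legitimate outcome for patients and for the department. Both statements are right, and the point is confined to precision.

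A second reply is that the inclusion of waiting time is inferred. That also stands in part. ED LOS has no stated start, and the inference rests on its being listed separately from post-rooming time. But a primary outcome with no defined start or stop needs a definition in any case.

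Third, the SDs and the correlation are assumed, so the benefit may be as small as the 6% row, or nearly nil with negative correlation. This stands.

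Three stronger readings are tempting, and the documents do not support them:
- A reader might infer that allocation cannot change the wait before rooming. That holds only for time before the envelope is opened. The place of randomisation is not stated, and if some patients are randomised before being roomed, the arm could affect when they are roomed.
- A reader might infer that the variables already collected remove all of this noise. Post-rooming time still includes any interval from rooming to randomisation, and the time of randomisation is not on the data list.
- A reader might infer that three clocks in a non-blinded trial leave the primary open to choice after the fact. Section V.B names one primary, which maps to ED LOS. Extra timestamps on a data list are not competing primaries.

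**Conclusion.** The concern holds as a matter of efficiency. The planned primary comparison leaves pre-randomisation time in the outcome with no adjustment, and the plan gives its post-rooming variable no analytic role. The consequence is a wider confidence interval, not a biased estimate.

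Under the stated assumptions (30-minute effect, total SD 90 to 120 minutes, wait SD 30 to 60 minutes, zero correlation) the required size falls by 6% to 44%. The documents supply none of the SDs and no correlation, so this range shows what is possible and does not estimate this trial's loss. A positive correlation enlarges the gain. A negative one shrinks it, to zero at worst.

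The baseline figures above are for an independent-samples comparison. The plan names a paired t-test for the primary, which does not fit two independently randomised arms. That has to be corrected in any event, and the regression below does both jobs.

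A reader might also want inpatient boarding time removed from the outcome. The documents do not mention admission, so they give no basis for asking for that analysis.

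**What to change.** 1. Define ED length of stay as arrival to ED departure and keep it as the single primary outcome.
2. Record the time at which the envelope is opened.
3. Replace the paired t-test for the primary with a linear regression of ED length of stay on assigned arm, adjusted for arrival-to-randomisation time. Report the adjusted mean difference with a 95% confidence interval.
4. Use arrival-to-room time (ED LOS minus post-rooming LOS) as the covariate only where rooming precedes randomisation. Otherwise it contains time after allocation, and adjusting for it could remove part of the effect.
5. Define post-rooming LOS and time to discharge, and label both as supportive.

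The cost is one extra timestamp, a few sentences of analysis plan, and a regression in place of a t-test. Both LOS variables are already to be abstracted.

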### Patient satisfaction survey

	1 (Extremely Dissatisfied)	2 (Dissatisfied)	3 (indifferent)	4 (Satisfied)	5 (Extremely Satisfied)
Were you satisfied with the overall care you received today?					
Did you comfortable with your wait time while in the Emergency Department?					
Do you feel you got imaging of your shoulder in a timely fashion?					
Do you feel your physician discussed your diagnosis appropriately?					
Do you feel your physician updated you often enough?					
Do you feel that your physician explain all procedures in a way that was clear and you could understand?					

### Cost Analysis

Not necessary as patient's ultrasound exam will not be billed.

### Issues/misdiagnosis

Any concerns by patients or participants will be addressed by PI as soon as possible. We do not anticipate any issues or missed diagnoses.

## V. DATA ANALYSIS

#### A. Sample Size Considerations

1. This study will be a multicenter study. Due to the infrequent nature of this injury, the data collection phase will take place over several years.

#### B. Statistical Methodology

Descriptive statistics will be used to evaluate demographic variables. Categorical variables will be reported as n (%) and will be analyzed by chi-square or Fisher's exact test as appropriate. Normally distributed continuous variables will be reported as mean and standard deviation and will be analyzed by student's t-test. Non-normally distributed continuous variables will be reported as medians and interquartile range and analyzed using Mann-Whitney U test. The primary outcome of difference in average length of stay in the ED will be analyzed by paired students T-test. Secondary outcomes will be evaluated by paired student t-tests as well. Statistical analysis will be performed using SPSS® Software (version 24; 2016) and the level of significance set at p value less than 0.05.

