#### A. Diagnosis of dislocation

1. **Standard of Care (control):** Order shoulder x-rays as felt necessary for standard of care of diagnosis of shoulder dislocation and reduction (portable XR versus done in radiology)

**2. Ultrasound (experiment):** No x-rays ordered. Initial evaluation with ultrasound; may also evaluate nearby areas for concern of fracture. Order x-rays after ultrasound as seen fit for other injuries of diagnostic uncertainty.

B. Shoulder reduction: Per standard of care

C. Confirmation of Reduction

- Standard of Care (control):** Order shoulder x-rays as felt necessary for standard of care of reduction confirmation.
- Ultrasound (experiment):** Use ultrasound for reduction confirmation. No x-rays ordered unless ultrasound did not adequately confirm

D. Post-reduction care (sling, follow-up, etc.): Per standard of care

	Control Group	Experimental Group
Diagnosis of Dislocation	Standard of Care (x-ray)	Ultrasound
Shoulder Reduction	Per Standard of Care	Per Standard of Care
Confirmation of Reduction	Standard of Care (x-ray)	Ultrasound

B. Study Population:

*Inclusion Criteria:*

1. Patients who are 18 years of age or older; *and*
2. Present to the VCU Emergency Department between August 1, 2020 and December 31, 2022; *and*
3. Have clinical signs of uncomplicated shoulder dislocation; *and*
4. Agree to participation in the study; *and*
5. Provides a written consent to be included in the study.

*Exclusion criteria:*

1. Patients who have a level 1 or 2 trauma activation, and/or;
2. Patients who are pregnant, incarcerated, or unable to consent, and/or;
3. Patients who have a past medical history of shoulder replacement in dislocated shoulder; and/or
4. Provider Discretion

E. Assessment of Resources

*1. Has sufficient access to the study population:*

Emergency Medicine attending and resident physicians will perform the study. They will already be in the Emergency Department and therefore will be notified of a patient meeting inclusion criteria and immediately be able to complete study following consenting process.

*2. Has sufficient time to conduct and complete the study:*

This will be a long-term project in the emergency department. Not all ED physicians will be participating in this study. The resident physicians and a select group of attending physicians will receive a curriculum and conduct the study.

*3. Has adequate qualified staff members to conduct the study:*

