##### Study Procedure Data

Group assignment (control or experimental)  
Experience of person performing ultrasound if in experiment group  
Minimal: Minimal prior experience, sufficient training completed  
Moderate: Prior shoulder ultrasound experience  
Expert: Fellowship trained, or significant prior exposure

Type of sedation/block/analgesic given  
Intra-articular? Nerve block? Procedural sedation?

Technique of shoulder reduction performed

Number of x-rays ordered

If ultrasound group, what x-ray was ordered and why  
Portable?

Findings

Type of dislocation (anterior versus posterior)

Fractures identified  
Missed diagnoses

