### VII. STUDY LIMITATIONS

Potential selection bias based on the inclusion/exclusion criteria may reduce external validation. Theoretical user error could cause misinterpretation in ultrasound findings; this is a low risk, and has built in protection. It may be a challenge to get IRB approval across all institutions Missing data or incomplete data for specific fields may also present error.

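### Missed diagnoses, the harm most directly tied to omitting x-ray, has no definition, time window or common method of detection in the two arms, and no analysis names it

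*Combined protocol and SAP*

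**What the plan says.** Under Methods, the ultrasound arm starts without x-ray. For diagnosis, the instruction is "Order x-rays after ultrasound as seen fit for other injuries of diagnostic uncertainty". For confirmation of reduction it is "No x-rays ordered unless ultrasound did not adequately confirm". Control patients have x-rays at the clinician's judgement, and the summary table shows x-ray at both steps for that arm.

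Under Data Collection, Study Procedure Data, the list of findings includes fractures identified and then "Missed diagnoses", with nothing further on either. The later Issues/misdiagnosis paragraph adds "We do not anticipate any issues or missed diagnoses". Study Limitations says "Theoretical user error could cause misinterpretation in ultrasound findings; this is a low risk, and has built in protection".

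In Section II the primary objective is length of stay. The "secondary objectives of this study include evaluating patient satisfaction, providing a cost analysis, time to diagnosis, confirmation of reduction, and volume of x-ray reduction". Missed diagnoses is not among them.

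The Statistical Methodology section names no analysis for the field. Two general rules are nearby: "Categorical variables will be reported as n (%) and will be analyzed by chi-square or Fisher's exact test as appropriate", and "Secondary outcomes will be evaluated by paired student t-tests as well". No risk difference or confidence interval is planned for any outcome. The Data and Safety Monitoring section deals with storage and with de-identification once collection is complete.

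**The concern.** The trial asks whether x-ray can be left out to save time. If the stay is shorter and fewer films are taken, readers will next ask what was missed.

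Two things stand in the way of an answer. The first and more important is ascertainment. A control patient normally has a film against which the bedside judgement can be checked. An ultrasound patient has one only if the operator is in doubt or suspects another injury. An operator who is confidently wrong orders no film, and the protocol describes no look at the patient or the chart after discharge. Such a miss would go uncounted, and the arms would not be counted on the same footing.

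The second is reporting. For very few events, a test of equality gives nearly the same p-value whatever the sample size. It does not say how large an excess the data still allow, and p = 1 is easily misread as equal safety.

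**Working it through.** **Inputs.** The documents give no sample size, miss rate or detection rate. Everything below assumes equal arms of n = 50, 100 and 200 and two-sided 5% tests. There is no figure in the plan to reproduce.

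**1. What the categorical rule would yield**

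- *0 v 0.* Only one table is possible, so Fisher p = 1. Chi-square is undefined because the expected counts are zero.
- *1 v 0.* With equal arms the single event is equally likely in either arm, so both tables have probability 0.5 and Fisher p = 0.5 + 0.5 = 1.
- *3 v 0.* Fisher p = 2 × C(n,3)/C(2n,3). For n = 50 this is 2 × 19,600/161,700 = 0.242. For n = 100 and 200 it is 0.246 and 0.248.

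The p-value hardly changes over a fourfold range of n.

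**2. What an interval would yield**

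The exact two-sided 95% upper limit for 0/n is 1 − 0.025^(1/n). The Newcombe interval combines the Wilson limits (l, u) of each arm: lower = d − √[(p₁ − l₁)² + (u₂ − p₂)²], upper = d + √[(u₁ − p₁)² + (p₂ − l₂)²]. For 0/n the Wilson limits are 0 and z²/(n + z²). At n = 50 the upper one is 3.84/53.84 = 7.1%.

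| Ultrasound v control | n = 50 | n = 100 | n = 200 | Fisher p |
|---|---|---|---|---|
| 0 v 0: exact upper limit, ultrasound arm | 7.1% | 3.6% | 1.8% | – |
| 0 v 0: difference, points | ±7.1 | ±3.7 | ±1.9 | 1 / 1 / 1 |
| 1 v 0: difference, points | −5.3 to 10.5 | −2.8 to 5.4 | −1.4 to 2.8 | 1 / 1 / 1 |
| 3 v 0: difference, points | −2.1 to 16.2 | −1.2 to 8.5 | −0.6 to 4.3 | 0.24 / 0.25 / 0.25 |

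**3. What unequal detection would do**

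Assume, purely as illustration, that every control miss is found but only half of those in the ultrasound arm.

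- True rates 5% v 1%: the expected observed difference is 0.05 × 0.5 − 0.01 = 1.5 points, against a true 4.
- True rates 4% v 2%: 0.04 × 0.5 − 0.02 = 0, against a true 2.
- Chance of seeing no ultrasound miss when the true rate is 4% is (1 − 0.04 × detection)^n:

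| Detection | n = 50 | n = 100 | n = 200 |
|---|---|---|---|
| 100% | 13% | 1.7% | 0.03% |
| 50% | 36% | 13% | 1.8% |

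An interval around an under-detected count is centred in the wrong place. Reporting an interval therefore does not repair the ascertainment problem.

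**4. Would listing the field as a secondary outcome be enough?** No. The plan sends secondary outcomes to a paired t-test. The arms are independent, the outcome is binary, and for 0 v 0 the variance is zero, so the statistic is undefined.

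**The case against.** *The interval is a reporting preference.* Largely true. The categorical rule already gives n (%), from which any reader could compute an interval. A reader might infer that the information is lost for good, but that does not follow. What cannot be supplied afterwards from published counts is a common definition and window.

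*The plan never says a p-value is the inference for missed diagnoses.* Correct. A reader might take the chi-square or Fisher sentence as the planned analysis, but it follows a sentence on demographic variables and does not mention this field. The supportable statement is that no analysis names the field, and that this rule is the only one that would fit.

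*Safeguards exist.* They do: x-ray may be added for doubt, for other injuries or for inadequate confirmation, and ultrasound may be extended to look for fracture. A reader might infer that the ultrasound arm is unprotected or unsafe. The documents support neither. The safeguards work when the operator recognises uncertainty, so what remains is the confident misread, which Study Limitations accepts as possible.

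*Other fields help.* Confirmation of reduction, a named secondary objective, partly covers persistent dislocation. Fractures identified, if recorded in both arms, gives an indirect comparison without later chart review. Neither counts misses directly. The layout of the findings list also does not settle whether these fields apply to both arms, which is a further reason to say so.

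*The numbers are invented.* The sizes and rates are assumptions, and the 50% detection figure is an illustration. The statement that no misses are anticipated is a general expectation, not a projected count. The Fisher result for 0 v 0 and 1 v 0 needs only equal arms.

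**Conclusion.** The point holds as a gap in ascertainment first and in reporting second. The field most directly tied to the risk of omitting x-ray is collected but undefined, has no follow-up window, is not a named outcome, and may be detected less completely in the arm where it matters most. A low or zero count could then reassure more than it should.

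At an assumed 50 to 200 per arm, a 0 v 0 result would leave differences of up to 7.1 to 1.9 points compatible with the detected counts. If only half of the ultrasound misses were found, a true 4% miss rate would show no case with probability 36% to 1.8%, instead of 13% to 0.03%.

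A reader might go further and conclude that the main result is compromised. It is not: the length-of-stay comparison does not depend on this field. This is a cheap improvement that should be made, not a flaw that invalidates the trial.

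**What to change.** 1. In Section II, name missed diagnoses as a safety outcome with one definition and one window for both arms. For example: a fracture, or a persistent or misclassified dislocation, not recognised at ED discharge and first documented within 30 days. The 30 days is a suggestion.
2. Find cases by the same chart review in both arms, completed before the data are de-identified.
3. In Statistical Methodology, exempt this outcome from the paired t-test. Report n/N in all randomised patients by assigned arm, with the risk difference and Newcombe 95% interval, and the exact 95% upper limit for the ultrasound arm if no case is seen there.
4. Record fractures identified in both arms and show them by arm as an indirect check.
5. State that a non-significant difference is not evidence of equal safety and that the interval covers detected misses only. Place this result beside length of stay.

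**Cost.** A few sentences, one table and one later chart look per patient. Chart review and record abstraction are already planned, but a post-discharge window is new, and an IRB amendment may be needed if the consent does not cover it. Misses treated elsewhere or never recorded will remain unseen, and the interval will probably be wide. No extra patients or clinical procedures are required.

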## III. METHODS

This study is a prospective, randomized, non-blinded evaluation of the use of ultrasound to diagnosis shoulder dislocation in emergency departments. The study population will consist of patients aged 18-65 that present to the VCU Emergency Department between August 1, 2020 and December 31, 2022 with suspicion of an uncomplicated shoulder dislocation.

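### The paired t-test named for length of stay cannot be run on independent arms, and the general Mann-Whitney rule does not exempt the primary outcome, so the replacement test is left open

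*Combined protocol and SAP*

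**What the plan says.** Everything that bears on the test is in one paragraph, V.B, Statistical Methodology. It opens with baseline data: "Descriptive statistics will be used to evaluate demographic variables". Two rules for continuous variables follow, with no stated limit to baseline data: "Normally distributed continuous variables will be reported as mean and standard deviation and will be analyzed by student's t-test", and "Non-normally distributed continuous variables will be reported as medians and interquartile range and analyzed using Mann-Whitney U test". The primary outcome then has its own sentence: "The primary outcome of difference in average length of stay in the ED will be analyzed by paired students T-test". The secondary outcomes follow: "Secondary outcomes will be evaluated by paired student t-tests as well".

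On design, section III states: "This study is a prospective, randomized, non-blinded evaluation of the use of ultrasound to diagnosis shoulder dislocation in emergency departments". Under Procedural Overview/Design, step 3 is: "Randomize patient with premade numbered envelopes stating standard of care or ultrasound protocol". Each patient is in one arm only, and no matching is described. Section II sets the primary objective as to "determine if there is any difference in the length of stay between patients with shoulder dislocation", which does not choose between means and medians.

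The paragraph does not say how normality will be judged, which rule prevails if length of stay is not normal, or what replaces the paired test.

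**The concern.** A paired test needs a within-pair difference, and this design supplies no pairs. The named primary analysis must therefore be replaced, and the same paragraph offers two replacements. One is the unpaired t-test, which keeps the average that the primary sentence names. The other is the general rule, which for skewed data leads to medians and Mann-Whitney.

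The two have different targets: a difference in mean minutes, or a shift in ranks reported beside medians. If the choice is made with the data in view, in a trial where arm is known to all, the primary verdict may depend on it. A rank result also need not answer a question about average stay. The ultrasound arm may go on to x-ray when the scan is inadequate or the diagnosis uncertain (section III, parts A and C), so a wider spread of stays in that arm is plausible.

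**Working it through.** **No plan figure to reproduce.** V.A, Sample Size Considerations, gives no sample size, SD, power or design effect. The significance level is 0.05 (V.B), taken here as two-sided. All other inputs are assumptions.

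**Step 1: can the named test be run?** The paired statistic is mean(d)/(SD(d)/√n), where d is a difference within a pair. With unmatched arms, d depends on an arbitrary ordering, and with unequal arm sizes it is undefined for some patients. Assume lognormal stays, control mean 240 minutes, coefficient of variation (CV) 0.6 and 30 patients per arm. Re-pairing the same patients at random 50 times then changed the verdict in about 12% of trials with no difference, and in about 18% with a 30-minute difference.

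**Step 2: how often do the two replacements differ?** Assume control stay = 180·exp(s·Z) minutes, with Z standard normal, s (log-SD) from 0.4 to 0.8, and 30 to 100 patients per arm. The ultrasound arm is identical (no effect) or multiplied by 0.8 (20% reduction). Each simulated trial is tested by Welch t and by Mann-Whitney.

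With no true difference:
- Each test alone rejects in about 4 to 6% of trials.
- At least one of the two rejects in about 6 to 8% (0.064 at s = 0.4 and n = 30; 0.078 at s = 0.8 and n = 100).
- A fixed rule, with Shapiro-Wilk in each arm and then the matching test, rejects in about 4 to 6%.

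With a 20% reduction:

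| s | n per arm | Power, t | Power, Mann-Whitney | Verdicts differ |
|---|---|---|---|---|
| 0.4 | 30 | – | – | about 11% |
| 0.4 | 50 | – | – | about 9% |
| 0.4 | 100 | – | – | about 2% |
| 0.6 | 30 | 0.243 | 0.264 | about 11% |
| 0.6 | 50 | 0.389 | 0.429 | about 15% |
| 0.6 | 100 | 0.663 | 0.719 | about 15% |
| 0.8 | 100 | 0.385 | 0.476 | about 20% |

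The largest power gap shown is 0.476 − 0.385 = 0.091, or about 9 points.

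A second set of assumptions (control mean 240 minutes, CV 0.4 to 0.8, 20 to 100 per arm, 30-minute difference) gave 5 to 14% disagreement. With no difference, it gave 5.7 to 7.3% for at least one test significant. The 30 minutes is the effect of diagnostic radiographs on stay cited in section I; the plan does not use it as a design effect.

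**Step 3: would the Mann-Whitney branch be reached?** If the general rule applied and normality were checked by Shapiro-Wilk, both arms would pass in at most about 2% of trials at s = 0.6, but in about 20% at s = 0.4 with 30 per arm. The plan names no normality test, so this is illustrative.

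**Step 4: do the two tests answer the same question?** A lognormal mean is median × exp(s²/2). With equal means and s = 0.4 (control) against 0.8 (ultrasound), the ratio of medians is exp((0.16 − 0.64)/2) = exp(−0.24) = 0.79. The ultrasound median is about 21% lower although average stay is identical. In simulation, Mann-Whitney rejected in about 45% of trials at 50 per arm and 74% at 100. Welch rejected in about 6%.

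**The case against.** The strongest reply is that the plan does assign the primary outcome a test. The sentence names the outcome, names a t-test and sets no normality condition, and a specific sentence ordinarily governs over a general one. The general rules follow a sentence about demographic variables, and they would still have work to do there, on age and weight for example. On that reading, deleting the word paired leaves one runnable test, and only an over-literal use of the general rule remains. Most of this stands. The ambiguity bites mainly through the pairing defect and is not a separate fault of equal weight. What survives is that the limit to demographics is not written into the general rules, no exemption is stated, and the named test has to be replaced in any case.

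A reader might infer that the plan permits two equal primary tests and so does not hold its 5% level. The documents do not support that. Nothing in them allows both tests to be run and the better one reported, and the 6 to 8% figure needs exactly that conduct. Nor do the tests often disagree: under a 20% reduction the range is roughly 2 to 20%, and the low end belongs to less skewed stays in larger samples.

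It is also fair to say that right-skewed stays are an assumption that the documents do not state, and that Welch rather than Student is a preference.

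**Conclusion.** The point holds as a clarification to be made with the pairing correction. The primary test cannot be run as named, and the paragraph does not settle whether its replacement compares means or ranks. The effect on type I error is small: about 6 to 8% under free choice of the better test, and about 4 to 6% under a normality rule fixed in advance. The firmer reason to act is the target of the analysis. When spreads differ, a rank test can report a shorter stay while the averages are equal, and the plan's stated outcome is the average. All sizes rest on assumed lognormal stays with 20 to 100 patients per arm. The equal-means result rests further on an assumed doubling of log-SD in the ultrasound arm.

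**What to change.** In V.B, replace the primary-outcome sentence with wording to this effect: *The primary outcome is the difference in mean ED length of stay (minutes) between the randomised arms, tested by a two-sample unpaired t-test (for example Welch) and reported with a 95% CI, regardless of the observed distribution. The normality-dependent rule for continuous variables does not apply to this outcome. Medians with interquartile range and a Mann-Whitney test are supportive only and do not decide the primary conclusion.*

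This keeps the plan's own endpoint and should be settled before outcome data are examined by arm. It costs one or two sentences, with no new data or patients. The downside is somewhat lower power than the rank test if stays are strongly skewed, about 0 to 9 points in the assumed scenarios.
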